6.2.4 Preparation

Preparation of the investigational product [PMT-002 (Suspension)] will be performed at the PMT manufacturing facility at the University of Pennsylvania. PMT-002 is packaged in EVA

bags suitable for storage at < -70°C (target -80°C). The investigational products will be packaged in single doses.

6.3 Measures to Minimize Bias: Randomization and Blinding

Neither subjects nor investigators will be blinded.

7 STUDY INTERVENTION DISCONTINUATION AND PARTICIPANT DISCONTINUATION/WITHDRAWAL

7.1 Participant Discontinuation/Withdrawal from the Study

Participants are free to withdraw from participation in the study at any time upon request and without impact to their regular medical care, but they will receive no further treatment with this investigational product.

An investigator may discontinue or withdraw a participant from the study for the following reasons:

- Significant study intervention non-compliance.
- If any clinical adverse event (AE), laboratory abnormality, or other medical condition or situation occurs such that continued participation in the study would not be in the best interest of the participant.
- If the participant meets an exclusion criterion (either newly developed or not previously recognized) that precludes further study participation.

The reason for participant discontinuation or withdrawal from the study will be recorded on the Case Report Form (CRF). Subjects who sign the informed consent form and do not receive FMT will be replaced.

7.2 Lost To Follow-Up

A participant will be considered lost to follow-up if they fail to return for greater than 2 scheduled visits and is unable to be contacted by the study site staff.

The following actions must be taken if a participant fails to return to the clinic for a required study visit:

• The site will attempt to contact the participant and reschedule the missed visit within 2 weeks and counsel the participant on the importance of maintaining the assigned visit schedule and ascertain if the participant wishes to and/or should continue in the study.

• Before a participant is deemed lost to follow-up, the investigator or designee will make every effort to regain contact with the participant (where possible, 3 telephone calls and, if necessary, a certified letter to the participant's last known mailing address or local equivalent methods). These contact attempts should be documented in the participant's medical record or study file.

• Should the participant continue to be unreachable, he or she will be considered to have withdrawn from the study with a primary reason of lost to follow-up.

8 STUDY ASSESSMENT AND PROCEDURES

8.1 Efficacy Assessments

8.1.1 Screening Visit

Potential candidates will be evaluated for eligibility per sections 6.1 and 6.2 and written informed consent will be obtained. Consented participants will be required to complete the following forms during their Baseline visit:

- Consent
- Eligibility Check List (includes St. Mark's Vaizey questionnaire)
- Pregnancy Test (if childbearing age)

If eligible, the following will be completed:

• Dietary Screener

• Questionnaires (Demographics, Medical History, SF-12, PFDI-20, ABLe Questionnaire, FIQL, Bristol Stool Index, PFIQ-7, Adaptation Index, PACSYM)

- Abbreviated Physical Exam
- Medication Log

Subjects will also be required to take the following home to complete prior to their treatment visit.

- One-week BM diary
- Stool Collection Kit (see stand-alone collection instructions)

8.1.2 Visit 1: Treatment

At this visit, the study coordinator will collect the one-week BM diary and stool sample from the subject. The PI or another trained physician will meet with the patient. Vital signs will be done to document temperature, blood pressure, heart rate, and oxygen saturation. A nasogastric tube will be placed and secured. The subject will then be escorted to the radiology suite by the study coordinator. A chest x-ray will be performed to ensure adequate placement of the nasogastric tube. The PI or trained physician will confirm adequate placement of the tube with the attending radiologist. The subject will then be escorted back to the office suite by the study coordinator. The PI or trained physician will then administer the treatment. The PMT-002 product will be drawn into a syringe and the syringe will be connected to the nasogastric tube (NGT) and the product will be pushed into the tube until all of the FMT product is administered. The NGT will then be removed by the PI or trained physician. The subject will remain in the office for one hour following the administration of the PMT product.

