2.3 Risk/Benefit Assessment

2.3.1 Known Potential Risks

The main risks of this study are related to administration of the investigational product. The most severe possible risks include allergic reaction, donor-derived infection, aspiration, and death. Other risks include nausea, vomiting, abdominal pain, diarrhea, flatulence, and fever.

As noted above, potential risks of the FMT treatment for FI includes gastrointestinal symptoms (including fever, aspiration, belching, bloating, nausea or vomiting, gastroesophageal reflux, abdominal cramps, abdominal pain, diarrhea, constipation). This is the first attempt to administer FMT for FI in women, however the risks are not expected to be significantly different from that reported in the literature.

Theoretical long-term risks may include: changes in metabolism, weight changes, development of autoimmune conditions.

Other risks include loss of privacy or confidentiality, as a result of study staff interacting with subjects.

These risks will be discussed with subjects during the informed consent process. The eligibility criteria will help mitigate these risks (e.g., excluding subjects with neutropenia or bowel perforation, and not permitting subjects at risk for aspiration to receive investigational product via upper gastrointestinal delivery). To minimize the risk of privacy and confidentiality loss, the minimum number of required study staff will interact with subjects, and all collected data will be protected as above.

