8.1.2.1 Post-PMT Administration monitoring: Bedside for 60 Minutes

Subjects will be monitored at 30 and 60 minutes following completion of PMT administration. Subjects will be visually observed for signs of aspiration or other respiratory distress, abdominal pain, vomiting, other signs of allergic reaction, and changes in vital signs. Vital signs (temperature, heart rate, respiratory rate, blood pressure, and oxygen saturation) will be checked. The following vital sign changes will be recorded if observed: (1) heart rate increase or decrease by greater than or equal to 30 beats per minute; (2) respiratory rate increase or decrease by greater than or equal to 10 breaths per minute or if respiratory rate drops below 10 or increases above 25 (if respiratory rate not already outside these ranges); (3) temperature: increase or decrease by greater than or equal to 2 degrees Fahrenheit, or if temperature drops below 96°F or increases above 100.4°F (if temperature not already outside these ranges); (4) oxygen saturation decrease by greater than or equal to 5% (sustained for more than 20 seconds) or if oxygen saturation drops below 90% (on current amount of oxygen delivered, sustained for more than 20 seconds); (5) blood pressure decrease by more than 30 mmHg systolic or 15 mmHg diastolic, or if blood pressure drops below 90/60 (if blood pressure not already outside these ranges).

During the monitoring period, information will be solicited from the patient regarding the following adverse events associated with FMT including aspiration, belching, bloating, nausea, vomiting, gastroesophogeal reflux, abdominal cramps, abdominal pain, diarrhea, and constipation.

Subjects will be sent home with:

- Second one-week BM diary. The diary will include a card for the collection of all solicited adverse events.
- Thermometer

- Temperature and Adverse Events log form
- Stool Collection Kit

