8.3.3.3 Expectedness

We expect that gastrointestinal symptoms (including fever, aspiration, belching, bloating, nausea or vomiting, gastroesophageal reflux, abdominal cramps, abdominal pain, diarrhea, constipation) may be common post administration of the investigational products, both as a consequence of the underlying disease being treated, and potentially as an adverse effect of the administered product.

In the initial, 60-minute bedside observation period following administration of investigational product, subjects will be monitored with close attention to the following:

- allergic reaction (temperature, skin rash, heart rate, or blood pressure change as already described)
- sepsis or shock (temperature, heart rate, or blood pressure change as already described)
- bowel injury (abdominal pain change)
- aspiration (respiratory rate or oxygen saturation change)
- gastrointestinal symptoms (belching, bloating, nausea, vomiting, GERD, abdominal cramps, abdominal pain, diarrhea, and constipation)

In the subsequent, 7-day monitoring period following administration of investigational product, subjects will be monitored with close attention to the following:

- donor-derived infection (temperature or abdominal pain change)
- gastrointestinal symptoms (aspiration, belching, bloating, nausea, vomiting, GERD, abdominal cramps, abdominal pain, diarrhea, and constipation)

In the subsequent, 28-, 48-, and 180-day monitoring periods, subjects will be monitored with close attention to the following:

- transmitted infection (temperature or abdominal pain change as already described)
- metabolic changes (polydipsia, polyuria, weight gain, or weight loss)

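### Section 8.1.2 requires no respiratory rate before FMT, so the 10-breath change rule in section 8.1.2.1 has no pre-treatment reference

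*Combined protocol and SAP*

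**What the plan says.** Section 8.1.2 describes the treatment visit in order. It says that vital signs are taken to "document temperature, blood pressure, heart rate, and oxygen saturation", and the step that follows is "A nasogastric tube will be placed and secured". The four signs listed are therefore the pre-treatment set.

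Section 8.1.2.1 covers the hour after dosing. At 30 and 60 minutes it checks five vital signs: the same four plus respiratory rate. For respiratory rate it gives two recording rules:

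- a change rule: "respiratory rate increase or decrease by greater than or equal to 10 breaths per minute";
- absolute limits: a rate below 10 or above 25, qualified by "if respiratory rate not already outside these ranges".

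Section 8.3.3.3 says what the reading is for. Among the events to watch in the 60-minute observation it lists "aspiration (respiratory rate or oxygen saturation change". Section 2.3.1 states: "The most severe possible risks include allergic reaction, donor-derived infection, aspiration, and death".

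**The concern.** A change needs two readings. The protocol sets a numeric threshold for a change in respiratory rate but requires only the later reading. The qualifier on the absolute limits has the same problem, because it asks whether the rate was already outside 10–25. Without a pre-dose value, a post-dose rate of 27 cannot be classed as new or pre-existing.

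Section 8.1.2.1 also does not say which reading any of its changes are measured from. For the other four signs the section 8.1.2 values are the obvious reference. For respiratory rate there is nothing to fall back on.

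At stake is one of the two vital-sign signals that the protocol assigns to aspiration, in a study that gives the product by syringe through a nasogastric tube. The efficacy analysis and the sample size are not affected.

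**Working it through.** **Step 1: compare the two lists.**

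| Vital sign | Required before FMT (8.1.2) | Checked at 30 and 60 min (8.1.2.1) | Change rule (8.1.2.1) |
|---|---|---|---|
| Temperature | yes | yes | yes |
| Blood pressure | yes | yes | yes |
| Heart rate | yes | yes | yes |
| Oxygen saturation | yes | yes | yes |
| Respiratory rate | **no** | yes | yes |

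Four signs are listed before dosing and five after. The difference is respiratory rate alone.

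**Step 2: look for a pre-dose rate elsewhere.** The screening visit (8.1.1) includes an abbreviated physical examination, and the schedule has a vital signs row. Neither lists components. Section 8.2 adds pregnancy tests, a temperature log and an adverse event card. None of these requires a respiratory rate.

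**Step 3: can the 30-minute reading serve as the reference?** Only for the 60-minute reading. Section 6.1.2 allows 10 to 90 minutes for administration, and the first check comes 30 minutes after completion. That is 10 + 30 = 40 to 90 + 30 = 120 minutes after dosing starts. A change already present by then would be built into the reference.

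**Step 4: what does the change rule add to the absolute limits?** Let *b* be the pre-dose rate and *p* the post-dose rate, both whole numbers within 10–25, so that the absolute limits are silent. The change rule fires when |*p* − *b*| ≥ 10.

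- Rises: *b* = 10 allows *p* = 20 to 25 (6 values), *b* = 11 allows 5, and so on down to *b* = 15, which allows 1. Total 6 + 5 + 4 + 3 + 2 + 1 = 21.
- Falls: by symmetry, from *b* = 20–25 to *p* = 10–15, another 21.
- *b* = 16 to 19: none. The smallest qualifying rise reaches 16 + 10 = 26 and the smallest qualifying fall reaches 19 − 10 = 9, and both cross an absolute limit.

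So 21 + 21 = 42 of the 16 × 16 = 256 in-range pairs are caught by the change rule alone. This counts combinations and is not a probability; the documents give no distribution of respiratory rates.

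**Example.** A participant goes from 13 before dosing to 24 at 30 minutes. The change is 24 − 13 = 11, which meets the rule. Since 24 lies within 10–25, no absolute limit is crossed. If only the required readings are taken, the rise cannot be identified.

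**The case against.** The strongest objection concerns weight; the text itself is not in dispute.

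- **Other checks cover aspiration.** Tube position is confirmed by X-ray and a physician gives the dose. Participants are "visually observed for signs of aspiration or other respiratory distress". Oxygen saturation has a pre-dose reading, a change rule and an absolute limit, and aspiration is a solicited adverse event. This stands, and it limits the consequence.
- **Nothing downstream uses the flag.** The primary safety endpoint in section 3 counts adverse events, and the pauses in section 8.3.8 rest on deaths, infections and graded or serious events. This also stands.
- **An uncheckable qualifier errs on the safe side.** If nobody knows whether a rate was already out of range, the likely result is over-recording. That is fair for the absolute limits. It does not help the change rule, where the error is a missed record.
- **Other study documents may require the count.** The protocol mentions manuals of procedures, case report forms and visit checklists, which are not available here. Sites may well count breaths anyway. But section 8.1.2 is the only text that itemises the pre-dose set, and it leaves respiratory rate out.
- **The omission looks like drafting rather than a deliberate choice.** That is plausible, but the rule still lacks its reference and the remedy is the same.

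**Conclusion.** The concern holds. As written, the protocol requires no respiratory rate before FMT, so the 10-breath change rule has no pre-treatment reference and its companion qualifier cannot be checked.

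The loss is confined to one recorded flag. For starting rates within 10–25, it affects only rises from 10–15 to 20–25 and falls from 20–25 to 10–15. How many of the 15 planned participants might show such a change cannot be estimated from the documents.

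The change should be made because a stated safety rule, tied to a risk the protocol ranks among the most severe, does not work as written, and because a pre-dose reading that was not taken cannot be recovered later. The conclusion assumes that sites do what the protocol text says and that no study document outside this protocol requires the missing reading.

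**What to change.** 1. In section 8.1.2, add respiratory rate to the vital signs taken before tube placement.
2. In section 8.1.2.1, state that the readings taken before tube placement are the reference for every change rule and for every qualifier about values already out of range. For the other four signs this is only clarification.

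The cost is one extra bedside breath count per participant and a short wording change in two adjacent subsections. The case report form for the treatment visit should have a field for the reading if it does not already.

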8.1.2.1 Post-PMT Administration monitoring: Bedside for 60 Minutes

Subjects will be monitored at 30 and 60 minutes following completion of PMT administration. Subjects will be visually observed for signs of aspiration or other respiratory distress, abdominal pain, vomiting, other signs of allergic reaction, and changes in vital signs. Vital signs (temperature, heart rate, respiratory rate, blood pressure, and oxygen saturation) will be checked. The following vital sign changes will be recorded if observed: (1) heart rate increase or decrease by greater than or equal to 30 beats per minute; (2) respiratory rate increase or decrease by greater than or equal to 10 breaths per minute or if respiratory rate drops below 10 or increases above 25 (if respiratory rate not already outside these ranges); (3) temperature: increase or decrease by greater than or equal to 2 degrees Fahrenheit, or if temperature drops below 96°F or increases above 100.4°F (if temperature not already outside these ranges); (4) oxygen saturation decrease by greater than or equal to 5% (sustained for more than 20 seconds) or if oxygen saturation drops below 90% (on current amount of oxygen delivered, sustained for more than 20 seconds); (5) blood pressure decrease by more than 30 mmHg systolic or 15 mmHg diastolic, or if blood pressure drops below 90/60 (if blood pressure not already outside these ranges).

During the monitoring period, information will be solicited from the patient regarding the following adverse events associated with FMT including aspiration, belching, bloating, nausea, vomiting, gastroesophogeal reflux, abdominal cramps, abdominal pain, diarrhea, and constipation.

Subjects will be sent home with:

- Second one-week BM diary. The diary will include a card for the collection of all solicited adverse events.
- Thermometer

- Temperature and Adverse Events log form
- Stool Collection Kit

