2.2.3 Dosing Rationale

There are no pre-clinical or clinical data for treatment of FI with FMT product to inform optimal dose. Thus, we have relied on the standard dosage used in other disease states. There are extensive observational studies and several randomized trials that suggest an FMT dose derived from 30-100g of human stool is effective to treat other conditions including Irritable Bowel Disorder and recurrent CDI (Johnsen Lancet 2018; Halkjaer Gut 2018; van Nood NEJM 2013; Youngster JAMA 2014; Kelly CR 2016).

The dose of the PMT investigational product to be employed in this study is based on the use of FMT in prior human studies (See Table 1). A single dose of up to 40g of donated stool, prior to processing into the final form, has been shown to be efficacious in these studies. The PMT products produced from these 40g stool mass contain a range of $1 \times 10^8 - 1 \times 10^{12}$ anaerobic bacterial CFUs. Given the lack of data for women with FI, we will use the dose that has previously been shown to be efficacious in recurrent CDI.

Table 1: FMT dosing and associated risks.

Authors	Publication Year	Population	Study Design	FMT Dose (g stool)	FMT Formulation	FMT Administration	Risks
Hamilton et al	2012	R-CDI	single-group trial	50g stool	250mL suspension	colonoscopy	diarrhea, flatulence
van Nood et al	2013	R-CDI	randomized trial	(not reported)	500mL suspension	duodenal tube	diarrhea, cramping, belching
Youngster et al JAMA	2014	R-CDI	single-group trial	48g stool	30 capsules	oral	cramping, bloating
Kelly et al	2016	R-CDI	randomized trial	64g stool	500mL suspension	colonoscopy	chills, abdominal pain, bloating, nausea, flatulence
Kao et al	2017	R-CDI	randomized trial	80-100g stool	40 capsules or 180mL suspension	oral or colonoscopy	nausea, vomiting, fever, abdominal discomfort
Weingarden et al	2013	R-CDI	case series	50g stool	250mL suspension	colonoscopy	(not reported)
Agrawal et al	2015	R-CDI	case series	~30-60g stool	150-500mL suspension	upper endoscopy, lower endoscopy, enema	diarrhea, constipation, abdominal pain, ileus
Aroniadis et al	2015	R-CDI	case series	(not reported)	suspension	upper endoscopy, lower endoscopy, enema, colonoscopy	diarrhea, abdominal pain
Fischer et al	2015	R-CDI	case series	50-100g stool	300mL suspension	sigmoidoscopy or colonoscopy	treatment failure and death
Fischer et al	2017	R-CDI	case series	50-100g stool	300mL suspension	sigmoidoscopy or colonoscopy	treatment failure and death

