3 STUDY OBJECTIVES AND ENDPOINTS

OBJECTIVES	ENDPOINTS
Primary	
Determine if fecal microbial transplantation leads to clinical improvement in refractory fecal incontinence in older women.	Number of subjects that show significant improvement at 4 weeks after FMT, and will be maintained at 12 weeks, relative to baseline using the St. Mark's Vaizey score, a measure of fecal incontinence severity.
Primary Safety	
Determine the safety of FMT administration via naso-gastric tube in older women with FI.	Frequency of adverse events, serious adverse events, and adverse events of special interest (including allergic reaction and gastrointestinal symptoms).
Secondary	
Determine if FMT leads to improved quality of life for subjects.	Number of subjects that have an improved quality of life at 4 and 12 weeks, measured by the FIQL scale.
Determine if the effectiveness of microbial engraftment following fecal microbial transplantation is associated with the degree of clinical improvement.	Concentration of microbiota present at baseline vs. at week 4 and at 12 weeks (optional)in subjects that demonstrate a significant improvement at 4 weeks after FMT, relative to baseline using the St. Mark's Vaizey score.
Tertiary	
Determine whether the baseline microbiota of the subject affects engraftment in fecal microbial transplantation for fecal incontinence.	Concentration of microbiota at baseline vs. concentration of microbiota at 4 weeks and at 12 weeks (optional).

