5.2 Exclusion Criteria

- Known food allergy that could lead to anaphylaxis
- Contraindications to nasogastric tube placement including:
 - Recent midface trauma
 - History of basilar skull fracture
 - Recent ENT surgery
 - Known coagulation abnormalities
 - Esophageal varices and/or esophageal strictures
- Untreated prolapse beyond the hymen
- History of Inflammatory Bowel Disease (does not include IBS)
- Unrepaired rectovaginal fistula/chronic 4th degree laceration
- Full thickness rectal prolapse
- History of congenital anorectal malformation
- History of bowel resection surgery for any indication
- Minor anal procedures within 6 months for treatment of accidental bowel leakage (ABL) (injection of bulking agent or radiofrequency energy) or ligation of hemorrhoids
- Prior pelvic or abdominal radiation
- Diagnosis of cancer of the descending colon or anus

```
FMT for FI
IRB#: 834196
```

- Clinically significant neurological disorders known to affect anal incontinence
- Chronic antibiotic use (>1 month continuous antibiotic)
- Pregnant or planning to become pregnant during the study duration 1 year
 - N/A if participant is not of childbearing potential
- Childbirth within the last 3 months
- Unwilling to use an acceptable form of birth control method if participant is of childbearing potential
 - N/A if participant is of not of childbearing potential
- Participation in another intervention trail impacting bowel function
- Inability to provide informed consent, complete questionnaires independently or to attend intervention sessions
- History of hepatitis C / HIV infection or other immunocompromised condition
- History of bowel resection surgery or pelvic irradiation
- Unable to speak, read, or write in English at a basic level
- In the opinion of the investigator not suitable for participation in the trial

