6.1.2 Dosing and Administration

A single dose of PMT-002 will be administered via a gastroduodenal tube over 10 to 90 minutes (target 30 minutes). In brief, nasogastric duodenal tube will be placed by a physician and its location will be checked by X-Ray. Once placement is confirmed, the PMT-002 product will be delivered via the NGT using a syringe attached to the end of the tube. Once the product has been delivered, the NGT will be removed. The patient will be observed for 1 hour in the office for potential adverse events.

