9.2 Primary	
Determine if fecal microbial transplantation leads to clinical improvement in refractory fecal incontinence in older women.	Our working hypothesis is that the St. Mark's Vaizey score, a measure of fecal incontinence severity, will significantly improve at 4 weeks after FMT, and will be maintained at 12 weeks, relative to baseline. A secondary outcome will be quality of life at 4 and 12 weeks.
Primary Safety	
Determine the safety of FMT administration via NG tube in older women with FI.	Our hypothesis is that there will be low occurrence of serious adverse events following administration of FMT via NG tube.
Secondary	
Determine whether the effectiveness of microbial engraftment following fecal microbial transplantation is associated with the degree of clinical improvement.	Our working hypothesis is that more transplanted strains will be present at 4 weeks in subjects with a higher response score.
Tertiary	
Determine whether the baseline microbiota configuration affects engraftment in fecal microbial transplantation for fecal incontinence.	Our working hypothesis is that the transplant will be more effective in baseline samples with lower microbial diversity.

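### Tube placement belongs to the primary safety objective, but placement events are recorded only unprompted and the SAE pause trigger names only the product (minor)

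*Combined protocol and SAP*

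**What the plan says.** **Objective and endpoint.** In section 3 the primary safety objective reads "Determine the safety of FMT administration via naso-gastric tube in older women with FI", and the endpoint is "Frequency of adverse events, serious adverse events, and adverse events of special interest". The hypothesis in section 9.2 is that "there will be low occurrence of serious adverse events following administration of FMT via NG tube". The route is part of the question.

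**The tube.** Under 6.1.2 a "nasogastric duodenal tube will be placed by a physician and its location will be checked by X-Ray". Section 8.1.2 adds a chest film, confirmation of position with the radiologist, and delivery by syringe. After dosing, "The NGT will then be removed by the PI or trained physician". Section 5.2 has a block headed "Contraindications to nasogastric tube placement including", with five bullets.

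**Solicited events.** Section 8.1.2.1 sets checks at 30 and 60 minutes after administration is complete. During that period "information will be solicited from the patient regarding the following adverse events associated with FMT including aspiration, belching, bloating, nausea, vomiting", followed by reflux, abdominal cramps, abdominal pain, diarrhea and constipation. The diary card collects the solicited events.

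**Other routes of capture.** Adverse events are reportable from consent to day 180 (8.3.6). They are sought by nondirective questioning and examination (8.3.5), on a take-home adverse event log (8.1.2.1) and at the one-week call (8.1.3).

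**Pause rule.** Section 8.3.8 lists five triggers. One needs an SAE related to the study product in two or more subjects. Another needs the same Grade 3 or higher event in two or more subjects and sets no condition on cause.

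**The concern.** The objective names the route, and the protocol treats the tube as a hazard when it selects patients. Yet no prompt asks about the step in which the tube goes in. A patient is asked about belching but not about a nosebleed or a sore throat, and the scheduled checks begin after insertion and infusion are over.

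The pilot is meant to supply safety data for a later randomized trial (section 4.1), and tolerability was one reason for choosing this route (section 4.3). If few placement events are recorded, a planner may conclude that the tube was well tolerated, when the count may partly reflect that nobody asked.

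The pause rule raises a related point. Section 8.3.5 records relatedness to treatment or process, and 8.3.6 names study procedures when it describes SAE reporting. The SAE trigger in 8.3.8 mentions the product alone.

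**Working it through.** The plan gives no figure on this point. Its only power-type figure, 1.59 standard deviations in section 9.3, concerns engraftment and has no bearing here. The check is a count of what is named, followed by an illustration under assumed rates.

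**1. Solicited list.** Section 8.1.2.1 names 10 items: aspiration, belching, bloating, nausea, vomiting, reflux, abdominal cramps, abdominal pain, diarrhea, constipation. The seven-day gastrointestinal line in 8.3.3.3 names the same 10. Placement events (nasal, throat, bleeding, insertion): 0 of 10. Route-related events: at least 1 of 10, because section 2.3.1 links aspiration to upper gastrointestinal delivery.

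**2. Tube hazards elsewhere.** The block in 5.2 has 5 bullets: midface trauma, basilar skull fracture, ENT surgery, coagulation abnormality, and esophageal varices or strictures. In Table 1 (section 2.2.3), 1 of 10 rows names a tube, and its risks are "diarrhea, cramping, belching". The table therefore offers no placement-event rate.

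**3. Timing.** The sequence in 8.1.2 is placement, x-ray, infusion, removal. The scheduled checks in 8.1.2.1 come at 30 and 60 minutes after infusion. Insertion lies inside the reporting period of 8.3.6 but before any scheduled check.

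**4. Routes of capture.** Placement events have four, all unprompted: the physician and coordinator present, nondirective questioning, the adverse event log and the one-week call. Gastrointestinal symptoms have these as well as the solicited list and card.

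**5. Why a low count is weak evidence (illustration only).** The 15 women come from section 9.3. The true rate p and the captured fraction c are assumptions. Expected recorded events = 15pc; chance that none is recorded = (1 − pc)^15. With p = 20%:

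| c | Expected recorded | Chance of none |
|---|---|---|
| 100% | 3.0 | 3.5% |
| 75% | 2.25 | 8.7% |
| 50% | 1.5 | 20.6% |
| 25% | 0.75 | 46.3% |

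Over p from 10% to 40% and c from 25% to 75%, the chance of none runs from 0.5% to 68.4%. With 0 of 15 recorded, the one-sided 95% upper limit is 1 − 0.05^(1/15) = 18.1% for the rate of recorded events. For the true rate it is 18.1%/c, which is 24.1% at c = 75% and 36.2% at c = 50%. Since c is unknown, a zero cannot be read at face value.

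**6. Pause triggers, for non-fatal tube harm judged unrelated to the product.**

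- Death attributable to FMT: not met.
- Suspected transmission of infection: not met.
- Same Grade 3 or higher event in two or more subjects: met if the two events are the same.
- Product-related SAE in two or more subjects: not met.
- Long-term events: not met.

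One trigger of five can apply. It misses two SAEs of different types, for example one bleed and one injury at insertion. It would also miss SAEs graded below 3, which is unlikely under the severity scale in 8.3.3.1.

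**The case against.** The other side has a good case, and much of it stands.

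- **Aspiration.** A reader might infer that no tube-related event is solicited. The documents do not support that. Aspiration heads the list, is watched for directly, and is tracked by respiratory rate and oxygen saturation (8.1.2.1, 8.3.3.3). The gap is confined to placement events.
- **Clinician presence.** A physician places and removes the tube, position is confirmed by x-ray before dosing, and events count from consent. A nosebleed at insertion happens in front of someone who can report it. This is why no loss of events can be asserted. It does not help with throat or nasal pain that the patient does not mention.
- **No planned comparison.** A reader might infer that a tube-versus-gastrointestinal comparison is invalidated. Section 9.4.1 plans only descriptive summaries, so there is no such comparison to invalidate. What remains is that the two kinds of frequency come from different ascertainment.
- **Wording of the list.** Its wording may be non-exhaustive, and section 10.1.8.1 says that case report forms and checklists will be developed. Placement items may appear there. The protocol does not require them.
- **Pause rule.** A reader might infer that tube SAEs go unreported or can never stop the trial. Every SAE reaches the sponsor within 24 hours whatever its cause (8.3.6), the same-Grade-3 trigger ignores cause, suspension is available at discretion (10.1.2), and a DSMB meets at least twice a year (10.1.5). These make the gap narrow. They do not make a pause automatic in the case described.

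**Conclusion.** A minor point that holds in two limited parts. First, the placement step of the route named in the primary safety objective is ascertained only passively: 0 of 10 solicited items concern it, and scheduled checks start after it. A low count of placement events would be weak evidence of good tube tolerability. The rates and capture fractions in the illustration are assumptions, so it shows the direction of the problem and does not estimate its size. The hypothesis about serious events is not affected by missed minor ones.

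Second, read as written, 8.3.8 would not force a pause after two different tube-related SAEs judged unrelated to the product. That rests on the trigger being applied literally. An investigator who counts the tube as part of the product's use would reach the other answer, which is itself a reason to settle the wording.

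**What to change.** 1. **Section 8.3.8.** Reword the SAE trigger so that it counts *an SAE related to the study product or its administration (including tube placement)*. Keep the two-subject threshold.
2. **Sections 8.1.2 and 8.1.2.1.** Record nosebleed, nasal or throat pain, gagging or coughing, and the number of insertion attempts, from tube insertion through 60 minutes after dosing. X-ray already checks position, so misplacement needs no new test.
3. **Solicited list and diary card.** Add nosebleed and nasal or throat pain for the first week. Without this, the difference in prompting would return once the patient leaves the office.
4. **Section 9.4.1.** Tabulate placement events separately from gastrointestinal symptoms.

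The cost is one phrase, a few recorded items, and more minor events in the tables. A pause becomes slightly likelier if tube SAEs are rare, in line with the protocol's hypothesis of low SAE occurrence. The size of the increase depends on a rate that the documents do not give. With assumed, independent risks per woman of 2% for a product SAE and 5% for a tube SAE, the chance that two or more of 15 meet the SAE trigger rises from 3.5% to 27.7% (per-woman risk 1 − 0.98 × 0.95 = 6.9%). That overstates the added pauses, because the same-Grade-3 trigger already catches repeats of one event. If tube SAEs were that frequent, a pause would be warranted.
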